## 2. Analysis of time to first event of HF hospitalizations (HHF) and of HHF/CV Death composite

### The VERTIS protocol and primary SAP already include (Tables and KM will be available):

- a) Secondary hypothesis superiority testing - time to the first composite of HHF/CV death as pre-specified efficacy outcome, which will be analyzed both in the intention-to-treat (CV ITT; primary analysis strategy) and the on treatment analysis (CV FAS with +14 and +30 days censoring window) utilizing Cox Proportional Hazard (CPH) statistical method.
- b) Secondary outcome of time to first Hospitalization for HF utilizing CPH model (CVITT and on treatment CV FAS + 14 days)
- c) **NEW: KM-individual treatment groups (5 mg, 15 mg) for HHF will be generated (KM - individual treatment groups for the composite already exists)**

### Additional proposed analysis will include (Tables and KM curves):

- I. Time to event analyses using Cox proportional hazards models will be performed for these assessments, using the Fine and Gray method to account for competing risk of non-CV mortality in analyses of the HHF/CV Death composite outcome (CV ITT) and HHF (CV ITT). Exposure times of all patients will be censored at the date they were last known to be free of all components of the individual and composite outcomes analyzed.
- II. A supportive analysis for the composite HHF/CV Death and HHF will be performed (CPH, CV ITT) in the subsets of patients with history of HF at baseline (1900/8238; 23.1%), and in those without prior HF. The time to first confirmed event will be modeled univariably with treatment, and also in multivariable analyses including region and baseline type of ASCVD status as ASCVD risk factors. Baseline CVD status /risk factors will include 5 different model terms:
  - o CAD,
  - o cerebrovascular disease,
  - o PVD,
  - o prior MI,
  - o prior stroke

In addition, univariable analyses CPH (CV ITT) with factor for HF at baseline will be conducted for:

- MACE;
- HHF/CV Death;
- CV death;
- HHF
- All-cause death

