With two enrollment periods of 19 months each and assuming an event rate of 3.5% per annum for MACE, a total of approximately 8000 subjects (about 4000 per enrollment cohort) randomized in a 1:1:1 ratio to ertugliflozin 5 mg, ertugliflozin 15 mg or placebo will be sufficient to accrue approximately 714 MACE events within approximately 5.0 years and approximately 939 MACE events within approximately 6.1 years from the start of this study. These calculations assume that subjects will withdraw from the study at a rate of 5% per annum.

Power for Secondary Hypotheses

For the Stage 2 analyses of secondary endpoints, using an O'Brien-Fleming alpha-spending approach and assuming accrual of at least 442 and 582 composite events of cardiovascular death or hospitalization for heart failure at the interim and final analysis respectively, the study will have approximately 90% power to demonstrate superiority of ertugliflozin to placebo on the composite of cardiovascular death or hospitalization for heart failure when the true HR=0.75. Moreover, assuming accrual of at least 287 and 377 cardiovascular death

events at the interim and final analysis respectively, the study will have approximately 83% power to demonstrate superiority of ertugliflozin to placebo on cardiovascular death when the true HR=0.725. With accrual of at least 144 and 190 renal composite events at the interim and final analysis respectively, the study will have approximately 79% power to demonstrate superiority of ertugliflozin to placebo on the renal composite endpoint when the true HR=0.65.

9.1.1. Sample Size for Insulin with or without Metformin Add-on Glycemic Sub-Study:

The sub-study is powered to demonstrate superiority of ertugliflozin compared with placebo in reducing HbA1c from Baseline to Week 18. It is estimated that a minimum of 450 subjects will be enrolled into the sub-study. The sub-study enrollment will not be allowed to exceed 50% of the overall trial sample size. The final determination of inclusion in the sub-study will be based on a programmatic assessment of the sub-study criteria.

In two recent studies of another SGLT2 inhibitor (dapagliflozin) in subjects with type 2 diabetes receiving high doses of insulin, estimates of the standard deviation of the change from baseline in HbA1c after 24 weeks ranged up to a maximum of 0.98%.^{15,16} Therefore, a standard deviation of 1.0% was taken as a conservative estimate for sample size calculations.

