Subjects without cardiovascular events will be censored at the earliest of the study cut-off date, last contact date, or end of the applicable analysis ascertainment window (eg, 365 days after the last dose for primary Stage 2 non-inferiority analyses).

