9.3. Secondary Endpoints Analysis

Secondary time-to-event endpoints (eg, fatal and non-fatal myocardial infarction, fatal and non-fatal stroke, hospitalization for heart failure, cardiovascular death, the composite of cardiovascular death or hospitalization for heart failure, the renal composite, and all-cause mortality) will be analyzed using Cox proportional hazards models with the same model terms as those included for the primary endpoint. A point estimate and two-sided nominal 95% confidence interval for the hazard ratio will be calculated based on the Cox model for

090177e187d04317\Approved\Approved On: 14-Mar-2016 14:12

each endpoint. Kaplan-Meier methodology will be used to estimate event rates over time for each treatment group.

If non-inferiority at the 1.3 margin is established for the primary MACE endpoint based solely on this study, then tests of superiority on the secondary endpoints of cardiovascular death or hospitalization for heart failure (composite), cardiovascular death (individual component), and the renal composite will also be performed. The population for superiority testing will include all randomized subjects and include all confirmed events, including those occurring more than 365 days following discontinuation of investigational product. Superiority tests will be implemented by comparing the upper bound of the appropriate alpha-adjusted two-sided CI to 1.0.

In order to control the Type I error rate across multiple hypotheses in Stage 2, a four-step hierarchical testing sequence for the pooled ertugliflozin group versus the placebo group will be utilized as follows:

1. Non-inferiority for MACE;
2. Superiority for cardiovascular death or hospitalization for heart failure (composite);
3. Superiority for cardiovascular death (individual component);
4. Superiority for composite of renal death, renal dialysis/transplant, or $\geq 2x$ increase in baseline serum creatinine.

If the result of the test at any step of the sequence is not statistically significant, then testing will stop so that tests further down in the sequence will not be conducted, and the corresponding null hypotheses will not be rejected. The alpha spending to be utilized for the interim and final analyses of the primary and secondary endpoints is described in [Section 9.7](#).

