**6. Absolute difference NNT table for the following outcomes:**

- MACE
- CV Death
- All cause mortality
- HHF
- HHF or CV Death

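### SAP Section 2, item I fits Fine-Gray models but names only Kaplan-Meier curves, which modestly overstate the risk of heart-failure hospitalization and do not correspond to the subdistribution hazard ratio

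*SAP*

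**What the plan says.** The SAP supplied is a heart-failure supplement to a primary SAP. The primary SAP itself is not among the documents, apart from excerpts in Appendix 2.

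- **Section 2, additional analyses.** The heading reads "Additional proposed analysis will include (Tables and KM curves". Item I covers HHF/CV death and HHF alone, "using the Fine and Gray method to account for competing risk of non-CV mortality". Item II and the analyses after it are Cox models in patients with and without prior heart failure.
- **Section 2, existing analyses.** These include "Secondary outcome of time to first Hospitalization for HF utilizing CPH model" and a new display: "KM-individual treatment groups (5 mg, 15 mg) for HHF will be generated".
- **Section 6.** "Absolute difference NNT table for the following outcomes" lists MACE, CV death, all-cause mortality, HHF, and HHF or CV death. It gives no estimator and no time point.
- **Protocol 9.3.** Secondary time-to-event endpoints are analyzed by Cox models, and "Kaplan-Meier methodology will be used to estimate event rates over time for each treatment group".
- **Protocol 9.2.** "Subjects without cardiovascular events will be censored at the earliest of the study cut-off date, last contact date", or at the end of the ascertainment window. A death that is not an endpoint event has no state of its own.

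No cumulative incidence or Aalen-Johansen estimate is named in the text supplied.

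**The concern.** Item I chooses Fine-Gray because death removes patients from the chance of a later heart-failure admission. A subdistribution hazard ratio is a statement about the cumulative incidence function. The only curve named for the item is Kaplan-Meier, which censors those deaths and so describes risk as if they did not occur. The model and the figure beside it would then describe different quantities, and the plotted HHF risk would be too high.

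Item I also names only non-CV mortality as competing. That suits HHF/CV death, where CV death is part of the outcome. For HHF alone, CV death competes as well and is probably the larger part.

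The supplement is written with publication in view. Readers will take HHF curves, absolute differences and NNT as actual risk, and the bias runs towards a larger apparent benefit.

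**Working it through.** **No figure to reproduce.** The documents give no HHF risk, cumulative incidence or NNT. What can be checked is the event counts used below. With 2:1 allocation, power = Φ(|ln HR|·√(D·2/9) − z). At two-sided alpha 0.044, D = 582 and HR 0.75 give 89.6% (Protocol: about 90%). D = 377 and HR 0.725 give 82.4% (Protocol: about 83%). The counts are usable.

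**Rates from the Protocol.** Section 9.1 plans 939 MACE, "assuming an event rate of 3.5% per annum for MACE", so 939/0.035 = 26,829 patient-years.
- HHF/CV death: 582/26,829 = 2.17% per year.
- CV death: 377/26,829 = 1.41% per year.
- First HHF: at least (582 − 377)/26,829 = 0.76% per year. This is a lower bound, because a patient with both events counts once in the composite.

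**Assumptions not in the documents.** Non-CV death 0.3 to 1.0% per year; HHF up to 1.2% per year; constant hazards; pooled planning rates used for placebo.

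**Formulas.** With event hazard h and competing-death hazard d:
- one minus Kaplan-Meier = 1 − exp(−ht)
- cumulative incidence = h/(h+d) × [1 − exp(−(h+d)t)]

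Example: h = 0.76%, d = 1.41% + 0.3% = 1.71%, t = 5. Kaplan-Meier gives 3.75%; cumulative incidence gives 0.309 × 0.116 = 3.59%.

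**Results at 5 years** (excess computed before rounding; ranges run over non-CV death 0.3 to 1.0%):

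| Outcome | Competing event | 1 − KM | Cumulative incidence | Excess, points | Relative |
|---|---|---|---|---|---|
| HHF, 0.76%/yr | all deaths | 3.75% | 3.59–3.53% | 0.15–0.22 | 4.3–6.1% |
| HHF, 1.2%/yr | all deaths | 5.82% | 5.58–5.49% | 0.24–0.33 | 4.3–6.1% |
| HHF/CV death, 2.17%/yr | non-CV death | 10.28% | 10.20–10.03% | 0.08–0.25 | 0.7–2.5% |

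For HHF at 3 years the excess is 0.06 to 0.12 points (2.6 to 3.6% relative). At 6.1 years it is 0.23 to 0.49 points (5.2 to 7.5%).

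**HF-history subset, hypothetical.** Take HHF 0.76%, CV death 1.41% and non-CV death 0.6% per year. Doubling all hazards gives 7.32% against 6.64% at 5 years (+10%). Tripling gives 10.77% against 9.33% (+15%).

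**NNT at 5 years, if it were taken from Kaplan-Meier.** NNT = 1/(placebo risk − ertugliflozin risk). HR 0.65 is the HHF result of the class trial cited in Protocol 1.3; 0.75 is the planning HR for the composite. For HHF, the cumulative-incidence ranges run over CV-death HRs of 0.725, 1.0 and 1.2.

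| Outcome | HR | NNT, KM | NNT, cumulative incidence |
|---|---|---|---|
| HHF, 0.76%/yr | 0.65 | 77.2 | 79.4–83.4 |
| HHF, 0.76%/yr | 0.75 | 108.3 | 110.6–118.2 |
| HHF, 1.2%/yr | 0.65 | 50.0 | 51.5–54.0 |
| HHF, 1.2%/yr | 0.75 | 70.3 | 71.7–76.7 |
| HHF/CV death | 0.75 | 40.5 | 40.8–41.5 |

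The Kaplan-Meier NNT for HHF is too low by about 2 to 8% (1 − 70.3/71.7 = 2.0%; 1 − 108.3/118.2 = 8.4%). For the composite it is too low by about 1 to 2%.

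**Share of the competing hazard for HHF.** CV death accounts for 1.41/(1.41 + 1.0) = 59% to 1.41/(1.41 + 0.3) = 82%. Item I as written leaves this part out.

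**The case against.** The supplement is declared exploratory and hypothesis-generating, no test or alpha depends on these curves, and at planning rates the bias is a fraction of a percentage point. All of that stands and limits the weight of the point.

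Four stronger readings are tempting, and the documents do not support them.

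- **That every Kaplan-Meier display here mismatches its model.** The existing HHF and composite curves, item II and Protocol 9.3 go with Cox models, which censor deaths in the same way. The mismatch is confined to item I. Elsewhere the only caution is against reading one minus Kaplan-Meier as absolute risk.
- **That the SAP derives its NNT from Kaplan-Meier.** Section 6 names no estimator. The only Kaplan-Meier-based absolute reduction and NNT shown is another trial's figure in the appendix of future analyses. The gap in Section 6 is an unstated method and time point.
- **That Kaplan-Meier would inflate the NNT.** It inflates the risk difference, so the NNT comes out too low.
- **That the distortion is large in patients with prior heart failure.** Assuming HHF 2.5% and death 6% per year, one gets 13.9% against 11.8% at 6 years and, with HR 0.70, an NNT of 25 against 30. Those rates have no source in the documents, and Section 6 plans no split by heart-failure history. The horizon is also too long. Planning figures imply about 26,829/8,000 = 3.4 years of mean follow-up. Randomization began in December 2013, so nobody had six years at the 14 October 2019 cut shown in SAP Appendix 2.

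**Conclusion.** The point holds for item I. As written, the plan sets Fine-Gray hazard ratios beside curves that estimate something else and that overstate HHF risk, and for HHF alone it omits CV death as a competing event. At 5 years the overstatement is about 0.15 to 0.33 points for HHF and at most about 0.25 points for HHF/CV death. The 10 to 15% relative figure for an HF-history subset is conditional on hazards two to three times the planning rates.

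The direction does not depend on the assumed rates: any competing death makes one minus Kaplan-Meier too high. The size rests on constant hazards, planning rates rather than observed ones, and the assumed non-CV death rate. The NNT result applies only if Kaplan-Meier is chosen for Section 6. This should be corrected before the displays are produced, but it does not touch the trial's confirmatory conclusions.

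**What to change.** 1. For item I, replace the Kaplan-Meier curves with Aalen-Johansen cumulative incidence curves. Treat all deaths as competing for HHF, and non-CV death as competing for HHF/CV death.
2. In the Fine-Gray model for HHF alone, name all-cause death as the competing event. Without this change, the new curve and the model would still describe different quantities.
3. Keep Kaplan-Meier beside the Cox analyses in Section 2 if wanted, with a note that it is not to be read as absolute risk.
4. In Section 6, compute the HHF and HHF/CV death absolute differences and NNT from cumulative incidence at one fixed time within follow-up, with 95% confidence intervals.

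The cost is SAP wording and a standard software option, with no new data. Absolute HHF effects will look slightly smaller.

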**Input from SAC members/co-authors**  
**Sponsor Co-authors:** PPD [REDACTED]

VERTIS CV is a multinational, placebo-controlled, double-blind, randomized, parallel-group Phase III trial to assess the impact of ertugliflozin therapy on cardiovascular (CV) outcomes in a population with type 2 diabetes mellitus (T2DM) and a history of atherosclerotic cardiovascular disease (ASCVD).

Here we describe the statistical considerations for additional exploratory analyses to further investigate the impact of ertugliflozin on heart failure (HF)-related outcomes to complement the primary assessment of HHF/CVD death in the primary statistical hierarchy and secondary outcomes of HHF. This document is a supplement to the HF hospitalization and related analyses in the protocol and the primary SAP, and is intended to prospectively specify a series of ‘hypothesis-generating analyses’. Additional exploratory analyses may be conducted in the future based upon the results of the pre-specified analyses of HF related outcomes.

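### For HHF alone, the Fine and Gray analysis leaves CV death out of the competing events, so it does not estimate the HHF subdistribution hazard ratio

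*SAP*

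**What the plan says.** SAP Section 2 first lists what the protocol and primary SAP already provide. Item b there is the "Secondary outcome of time to first Hospitalization for HF utilizing CPH model", so the cause-specific HR for HHF is already planned.

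Item I of the additional analyses then adds the "Fine and Gray method to account for competing risk of non-CV mortality in analyses of the HHF/CV Death composite outcome (CV ITT) and HHF". Both outcomes are analysed in CV ITT, and non-CV mortality is the only competing event given. The next sentence sets the censoring rule: "Exposure times of all patients will be censored at the date they were last known to be free of all components" of the outcomes analysed. It does not mention subjects who die of a competing cause. The heading over items I and II reads "Additional proposed analysis will include (Tables and KM curves").

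The SAP introduction says that the supplement should "complement the primary assessment of HHF/CVD death in the primary statistical hierarchy and secondary outcomes of HHF", and describes its analyses as hypothesis-generating. Neither Protocol Section 9.2 nor the primary SAP excerpt in SAP Appendix 2 gives a competing-event definition for HHF.

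**The concern.** A subdistribution HR describes the effect on the observed cumulative incidence of an event. To estimate it, every event that makes the outcome impossible has to be coded as competing. For the composite, non-CV death is the only such event. For first HHF there are two, CV death and non-CV death, and item I names one.

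A programmer who follows the text would code non-CV death as competing and let CV death end follow-up as censoring. The estimate then refers to a hypothetical setting in which non-CV death occurs and CV death does not. That is neither of the two standard quantities.

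The omitted cause is also the one for which the protocol hypothesises a drug effect (CV death HR 0.725, Section 9.1). A reader told that competing mortality was accounted for would assume that CV death was included.

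**Working it through.** Item I states no figure to reproduce, so the check covers the event counts borrowed from the protocol, how common CV death is relative to HHF, and how far the estimate moves.

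**1. Protocol inputs.** Section 9.1 gives, at interim and final, 442 and 582 composite events ("assuming accrual of at least 442 and 582 composite events of cardiovascular death or hospitalization for heart failure") and 287 and 377 CV deaths ("assuming accrual of at least 287 and 377 cardiovascular death"). I used information = events × 1/3 × 2/3, Schoenfeld drift, and two looks with O'Brien-Fleming-type spending:
- Composite, HR 0.75: power 90.0% (stated about 90%); interim power 70.2% (stated about 70%).
- CV death, HR 0.725: power 83.1% (stated about 83%).

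The borrowed inputs are consistent.

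**2. How common is CV death before HHF?** Let x be the number of CV deaths that follow an HHF.
- CV deaths before any HHF = 377 − x
- First HHF = 582 − (377 − x) = 205 + x

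The documents do not give x. For an assumed x of 0–150, there are 205–355 first HHF and 377–227 CV deaths without prior HHF. CV death is a frequent competing event.

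**3. A version that can be checked by hand.** Assumptions: constant hazards; x = 0; placebo hazards scaled from the protocol's 3.5% per year MACE and 939 events; non-CV death at 0.4 times the CV death rate; HHF cause-specific HR 0.75 (the protocol gives 0.75 for the composite only); CV death HR 0.725; no drug effect on non-CV death.

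- HHF: 205 × 0.035/939 = 0.00764 per year
- CV death: 377 × 0.035/939 = 0.01405 per year
- Non-CV death: 0.4 × 0.01405 = 0.00562 per year

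With HHF hazard h and total competing hazard k, S(t) = exp(−(h+k)t) and F(t) = h/(h+k) × (1 − S(t)). The subdistribution hazard is h × S(t)/(1 − F(t)). At two years S/(1 − F) is:

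| Competing events | Placebo | Ertugliflozin | Subdistribution HR |
|---|---|---|---|
| Non-CV death only (as written) | 0.98874 | 0.98876 | 0.75 × 0.98876/0.98874 = 0.7500 |
| All death | 0.9611 | 0.9687 | 0.75 × 0.9687/0.9611 = 0.7559 |

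The large-sample Fine and Gray solution over follow-up, with censoring assumed uniform over 2–6 years, gives 0.750 and 0.756. Six-year placebo HHF incidence from F(6) is 4.41% as written and 4.23% with all death competing. If every hazard is multiplied by four, as an illustrative high-risk subset, the HRs are 0.750 and 0.775, and the incidences 15.7% and 13.5%.

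**4. The trial's own design.** The Fine and Gray score equation was solved for 8000 subjects, 1:2 allocation, two 19-month cohorts, 5% per year withdrawal and cut-off at 6.1 years (protocol figures). Assumed: second cohort starts at 2.1 years, constant hazards, HHF HR 0.750, x 0–150, non-CV death 0.4–1.2% per year. The accrual model gives 987 MACE against 939 planned, so it runs about 5% high (987/939 = 1.05).

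| CV death HR | As written | All death competing |
|---|---|---|
| 0.725 | 0.7500–0.7502 | 0.754–0.757 |
| 0.85 | 0.7500–0.7502 | 0.752–0.754 |
| 1.0 | 0.7500–0.7502 | 0.750 |

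These rows assume no drug effect on non-CV death. If that HR is 0.85 or 1.15, the as-written result differs from the Cox HR by −0.0028 to +0.0031.

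**5. Incidence.** With CV death censored, five-year HHF incidence is overstated by 1.7–4.1% in relative terms. In the placebo arm at 0.8% per year non-CV death, it is 4.13% against 3.97% (x = 0) and 7.04% against 6.88% (x = 150). A 1 − KM curve, which censors every death, overstates it by 2.7–7.2%.

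**The case against.** The SAP never says in so many words that CV deaths are censored in the HHF model, and the full primary SAP is not available. The censoring sentence also covers components of the composite, so a CV death might be read as falling outside it. This stands as a caution. But item I does state a competing event for HHF, that statement is incomplete, and censoring is what follows if it is applied literally. If all-cause death was intended, the sentence still needs correcting.

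The effect is very small. With 205–355 HHF events at 1:2, the standard error of the log HR is 1/√(events × 2/9) = 0.15–0.11. The largest shift, 0.0072 on 0.750, is ln(0.7572/0.750) = 0.0096, under a tenth of a standard error. The incidence gaps in the examples are 0.16 percentage points. This stands, and it limits the weight of the point. It is equally true that the corrected HR moves little from the Cox result.

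CV death is visible elsewhere: the confirmatory composite includes it, and CV death and all-cause death are analysed separately. That reduces the practical harm but does not supply an HHF subdistribution HR.

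The KM heading covers item II as well, which is ordinary Cox regression, and no text ties KM plots to the Fine and Gray analysis. This is fair, so the request about curves is limited to the HHF display that accompanies item I.

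**Conclusion.** The concern holds. For HHF/CV death item I is right. For HHF alone it omits CV death, and following it does not give the subdistribution HR for HHF. If the drug has no effect on non-CV death, it returns the planned Cox HR to within 0.0002, so the added analysis tells the reader almost nothing new.

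Under the assumptions shown, correct coding moves an HR of 0.750 by +0.0043 to +0.0072 when the CV death HR is 0.725, and by 0.0001 when it is 1.0. The direction follows from the definitions. The size rests on assumed values for x, the non-CV death rate, the HHF HR, constant hazards and the second cohort's start. The shift would be larger in high-risk subsets. No confirmatory test is affected.

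**What to change.** In SAP Section 2, additional analyses, item I:

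- Name the competing event by outcome: non-CV death for HHF/CV death; death from any cause, CV or non-CV, for HHF alone.
- State that the censoring sentence applies to subjects alive and free of the outcome, and that subjects with a competing death are handled as competing events.
- For this analysis, show HHF as cumulative incidence curves with all-cause death competing. KM curves can stay with the Cox analyses.

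The cost is one sentence in the SAP, one line of code and one change of plot type. No data collection, sample size or confirmatory analysis changes.

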## 3. Total events (composite of HF hospitalization or CV death)

The classical analysis of time to first event has the disadvantage of excluding all events that occur subsequent to the first. In order to gain maximal information from the study, it is important to consider events that occur after a first non-fatal event has occurred.

- I. Analyses will be performed to explore the effect of ertugliflozin on total events including the first and subsequent events for HHF and HHF/CV Death outcomes. Anderson-Gill method will be used as the primary analysis method (CV ITT) to analyze multiple occurrences of these outcomes (1 event, 2 events,  $\geq 3$  events), with treatment as an explanatory factor, region as a stratification factor, and history of HF and CVD status at baseline as other factors. CVD status will include CAD, cerebrovascular disease, PVD, prior MI, and prior stroke. A point estimate and two sided 95% confidence interval for the hazard ratio and the resulting p value will be reported. Descriptive statistics will also be reported for recurrent events, displaying the number of patients with 1, 2, and  $\geq 3$  events) by treatment group.

Alternative methods for analyses of first + recurrent events, including Wei-Lin-Weisfeld (WLW) method, negative binomial regression and frailty models will not be used in initial analysis but will be provided as sensitivity analyses if requested by the peer review process.

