#### 4. Subgroup analyses (table /forest plots).

Analyses of time to first event of HHF and of HHF/CV death (CV ITT), pooled doses, stratified by the following baseline characteristics will be included, using formal test of heterogeneity of the treatment effect among these subgroups:

- Median split for age
- Sex
- Race
- Ethnicity
- Region
- Median split BMI
- Median split for diabetes duration
- Baseline  $\text{HbA1c}$  ( $< 8.5$ ,  $\geq 8.5$ )
- Baseline UACR ( $< 30$ ; 30-300; and  $> 300$ )
- Baseline ACEI/ARB
- Baseline MRA use
- Baseline beta blocker use
- Baseline loop diuretic use
- Baseline insulin use
- Baseline metformin use
- Prior HF
- Ejection Fraction ( $< 40\%$ ; 40-50%;  $> 50\%$ ; unknown EF)
- Prior MI (Yes/No)
- CAD (Yes/No)
- Atrial fibrillation
- Hypertension
- Baseline eGFR ( $< 45$ , 45-60, 60-90, and  $\geq 90$ ) and dichotomously by eGFR  $< 60$ : Y/N

**5. Additional analyses of time to first primary and key secondary outcomes (CV ITT population) by EF (< 45%; ≥45%; unknown):**

- a) among those with HF at baseline; and
- b) in the overall population regardless of HF history at baseline:

Forest plots will be available for primary and key efficacy outcomes based on presence or absence of prior HF at baseline.

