**Table 2. TRS-HFDM in the Derivation Cohort**

Risk Indicator	Adjusted HR (95% CI)	P Value	Points
Prior heart failure	4.22 (3.18–5.59)	<0.001	2
Atrial fibrillation	2.26 (1.62–3.14)	<0.001	1
Coronary artery disease	2.06 (1.45–2.93)	<0.001	1
eGFR <60 mL·min  ·1.73 m 	1.85 (1.40–2.46)	<0.001	1
Urine albumin-to-creatinine ratio			
>300 mg/g	4.50 (3.18–6.36)	<0.001	2
30–300 mg/g	2.08 (1.50–2.87)	<0.001	1

eGFR <60 mL·min·1.73 m^-2 represents chronic kidney disease. Urine albumin-to-creatinine ratio 30–300 mg/g represents moderately increased albuminuria, whereas >300 mg/g represents severely increased albuminuria. eGFR indicates estimated glomerular filtration rate; HR, hazard ratio; TIMI, Thrombolysis in Myocardial Infarction; and TRS-HFDM, TIMI Risk Score for Heart Failure in Diabetes.

Berg et al

Heart Failure Risk Stratification in Diabetes

**Figure 2. Treatment effect of dapagliflozin by baseline risk of hospitalization for heart failure.** Although relative risk reductions were similar across risk score categories, absolute reductions in Kaplan-Meier estimates of hospitalization for heart failure risk at 4 years were greater in those at higher baseline risk ( $\chi^2=3.24$ ; 1-sided P for trend=0.04). ARR indicates absolute risk reduction; HR, hazard ratio; and NNT, number needed to treat.

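### The supportive adjusted models for HHF and HHF/CV death leave out atrial fibrillation, eGFR and UACR: a small loss of precision for total HHF, and a small loss of power for first HHF

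*SAP*

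**What the plan says.** SAP Section 2, additional analysis II, fits Cox models for first HHF and first HHF/CV death, separately in patients with and without prior HF. Each is fitted with treatment alone and then in "multivariable analyses including region and baseline type of ASCVD status as ASCVD risk factors". The SAP adds that "Baseline CVD status /risk factors will include 5 different model terms": coronary disease, cerebrovascular disease, peripheral vascular disease, prior MI and prior stroke.

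Section 3.I specifies an Andersen-Gill model for total HHF and total HHF/CV death in the CV ITT population, "with treatment as an explanatory factor, region as a stratification factor, and history of HF and CVD status at baseline as other factors". CVD status there means the same five terms.

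Atrial fibrillation, eGFR and UACR appear in neither list. They are available at baseline: Section 4 names "Atrial fibrillation", baseline eGFR and baseline UACR as subgroup factors. Appendix 1 reproduces a published risk score for HHF in diabetes whose indicators include "Urine albumin-to-creatinine ratio". The SAP gives no reason for its choice of covariates.

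**The concern.** The adjustment set is described as risk factors for atherosclerotic disease, but the outcome modelled is heart failure. Covariates are most useful when they predict the outcome being analysed. The reproduced table gives these adjusted hazard ratios for HHF:

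| Indicator | HR | In the adjusted models? |
|---|---|---|
| UACR >300 mg/g | 4.50 | No |
| Prior HF | 4.22 | Yes: by the split in Section 2.II, as a term in Section 3.I |
| Atrial fibrillation | 2.26 | No |
| UACR 30-300 mg/g | 2.08 | No |
| Coronary artery disease | 2.06 | Yes |
| eGFR <60 | 1.85 | No |

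Three of the table's predictors are unused, including the one with the largest hazard ratio. At stake is a little information in analyses meant to extract as much as possible from the trial. The validity of any confirmatory test is not in question.

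**Working it through.** **1. The plan's nearest stated figure.** The documents give no precision figure for the adjusted HHF models. The closest is the power of about 90% for CV death/HHF (Protocol 9.1: 442 and 582 events, HR 0.75; alpha 2% then 4.4% two-sided in Protocol 9.7). With doses pooled the allocation is 2:1, so the expected z is sqrt(d × 2/9) × |ln HR|.

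- Interim: sqrt(442 × 2/9) × 0.2877 = 2.851, against a critical value of 2.326.
- Final: sqrt(582 × 2/9) × 0.2877 = 3.272, against 2.014.
- The two-look power is 90.03%, so the stated figure reproduces.

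The same formula shows what drives Cox precision. The standard error of the log HR is close to 1/sqrt(d × p(1-p)), with d the number of events and p the placebo share. Covariates do not enter it.

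**2. First-event Cox models (Section 2.II).** 400 trials were simulated per setting.

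- From the SAP: the hazard ratios above, CAD 75.9%, UACR 30-300 30.1%, UACR >300 9.1%, and HF subset size 1,933 (the SAP also gives 1,900 of 8,238).
- Assumed: atrial fibrillation 8-25%, eGFR <60 20-40%, HHF incidence as shown, follow-up 2-6 years, and independent covariates.
- Model A has treatment and CAD (plus HF when pooled). Model B adds the three omitted factors. Region and the other four ASCVD terms were not simulated.

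| Setting (true HR) | Log HR, A to B | SE, A to B | Power, A to B |
|---|---|---|---|
| Prior HF, 8% incidence (0.70) | -0.348 to -0.363 | 0.1641 to 0.1646 | 57.8% to 61.3% |
| Prior HF, 15% (0.70) | -0.337 to -0.362 | 0.1199 to 0.1203 | 78.2% to 83.5% |
| No HF, 2.5% (0.70) | -0.361 to -0.363 | 0.1625 to 0.1626 | 60.5% to 61.5% |
| No HF, 5% (0.70) | -0.367 to -0.373 | 0.1145 to 0.1146 | 88.7% to 89.0% |
| All patients, 3.5% (0.70) | -0.354 to -0.362 | 0.1201 to 0.1202 | 85.0% to 86.5% |
| Prior HF, 15% (1.00) | about 0 in both | 0.1249 to 0.1252 | no gain |

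The SE is flat or very slightly larger. In the null row, 291 events give 1/sqrt(291 × 2/9) = 0.124, which agrees. What changes is the estimate. In the HF subset the smaller model is attenuated by 1 - 0.3476/0.3632 = 4% to 1 - 0.3369/0.3616 = 7%; as hazard ratios, 0.706 against 0.695 and 0.714 against 0.697. Monte Carlo error on each power is 1.5-2.5 points, but A and B were fitted to the same simulated trials.

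**3. Total-HHF model (Section 3.I).** Here the robust variance contains between-patient variation in rates, so covariates can reduce it. For a rate model with robust variance, used as a proxy for Andersen-Gill, the variance relative to pure Poisson is:

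- existing terms: 1 + m × S × (O(1 + f) - 1)
- with the three added: 1 + m × S × O × f

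m is the mean number of events per patient and f the frailty variance. S and O are the products of E[h²]/E[h]² over the included and omitted factors, where h is a factor's hazard ratio.

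- S: prior HF (23.4%) 1.604 × CAD 1.063 = 1.706.
- O: atrial fibrillation (10%, assumed) 1.113 × eGFR <60 (22%, assumed) 1.088 × UACR 1.389 = 1.682. Unknown UACR is counted as reference.
- m: 350 total HHF (assumed)/8,246 = 0.0424.

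With f = 0 the ratio is 1/(1 + 0.0424 × 1.706 × 0.682) = 1/1.049, a 4.7% reduction. With f = 1 it is 1.122/1.171, a 4.2% reduction. Simulation of the same rate model gave 5.3%, 5.0% and 4.1% for f = 0, 1 and 3. At 250 events the simulated reduction is 3-4%. In SE terms, 1 - sqrt(0.96) = 2.0% and 1 - sqrt(0.95) = 2.5%. A variance reduction also appears when the true ratio is 1.0, so it is a real precision gain.

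**The case against.** The strongest counter-argument is that little depends on these models. The SAP describes its analyses as hypothesis-generating and item II as supportive. The unadjusted estimate is reported beside the adjusted one, and the formal HHF/CV death test in Protocol 9.3 uses a different model. All of that stands and keeps the point minor.

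The risk table comes from another study's derivation cohort and sits under possible later work in Appendix 1. It concerns HHF alone and so says nothing direct about HHF/CV death. That also stands: the table is reasonable evidence for choosing covariates, but its hazard ratios need not transfer to this trial.

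A reader might infer more than the documents support, in three ways:

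- That precision is lost in every adjusted HHF model. In the first-event Cox models the SE does not fall when the factors are added.
- That the plan ignores predictors of heart failure. It includes CAD, and prior HF is handled by the split or as a model term.
- That the larger reduction found for total HHF within the HF subset (about 6-8% in variance) applies to a planned analysis. Section 3.I specifies the whole CV ITT population with HF history as a factor. The later HF-by-EF list of total events covers HHF combined with death and names no covariates.

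**Conclusion.** The point holds as a low-severity improvement. The adjusted models omit three available baseline predictors of HHF, and no rationale is given.

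- **Total HHF:** the omission costs roughly 4-5% in variance (about 2-2.5% in SE), and 3-4% in variance if there are nearer 250 events.
- **First HHF:** the omission attenuates the hazard ratio. It costs about 3-5 points of power in patients with prior HF and 0-2 points elsewhere, and nothing if there is no treatment effect.
- **HHF/CV death:** no gain has been quantified.

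These sizes depend on assumed atrial fibrillation and eGFR prevalences, event counts, frailty and independent covariates, and on the external hazard ratios applying here. Not all the planned terms were in the simulated comparator models. The direction is more secure than the exact size.

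**What to change.** Before unblinding, add baseline atrial fibrillation, eGFR and UACR to the multivariable Cox models in Section 2.II and the Andersen-Gill model in Section 3.I, keeping region, the five ASCVD terms and HF history as they are. Enter UACR either in categories (<30, 30-300, >300, unknown) or as log UACR with a missing indicator, so that the 243 patients (2.9%) with unknown values stay in the analysis. If the sponsor prefers the present set, one sentence of rationale should be added.

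The variables are already needed for the Section 4 subgroups, so no new data are required. The cost is a short SAP edit, a few extra model terms and the rule for unknown UACR. The tables shown in the SAP are labelled blinded; making the change while that holds avoids any suggestion that covariates were chosen on the results.
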